5.7. Medical and Psychiatric History

Medical and psychiatric history events will be mapped to a Medical Dictionary for Regulatory Activities (MedDRA) version 27.0 or higher preferred term and system organ class.

Medical and psychiatric history will be summarized by treatment group using preferred terms and system organ classes. All events will be listed.

5.8. Exposure to Treatment

The number of days on study drug, reasons for premature discontinuation of IMP, treatment compliance, days in each phase (Titration and Maintenance), and average dose in each phase, will be summarized by treatment group for the FAS Population. Exposure data, including dose level as received, will be listed.

5.9. Primary Efficacy Analysis

5.9.1. Primary Estimand

The key research question for the primary endpoint will be addressed with an estimand based on the following attributes:

- 1) Treatments: treatments as randomized regardless of the actual treatment received or the final dose level achieved following the titration steps.
- 2) Target study population of interest: subjects in the modified intent-to-treat (mITT) population regardless the completion status of dose titration steps.
- 3) Endpoint (variable) of interest: change from baseline to Week 26 in the MDS-UPDRS Part II + III Combined Score.
- 4) Population level summary of interest: estimated mean difference between each tavapadon dose group and placebo group in the endpoint of interest.
- 5) Strategy for Intercurrent events (ICEs): a hypothetical strategy will be used to address intercurrent events (ICEs) of potential death, treatment discontinuations, missed visits/assessments, and start of prohibited concomitant Parkinson's disease medications. The data after treatment discontinuations or after the start of prohibited Parkinson's disease concomitant medications will be censored under the hypothetical strategy. Prohibited Parkinson's disease concomitant medications are defined as medications in ATC classifications of ADAMANTANE DERIVATIVES, DOPAMINE AGONISTS, MONOAMINE OXIDASE B INHIBITORS, OTHER ANTIPARKINSON DRUGS, OTHER DOPAMINERGIC AGENTS, or DOPA AND DOPA DERIVATIVES that are started after the first dose of IMP and prior to the last dose of IMP with duration of use 7 days or more. The hypothetical strategy allows the study to assess the effect of tavapadon treatment without the confounding effect of prohibited concomitant Parkinson's disease treatments.

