10.	Subjects who are treatment naïve or have a history of prior incidental treatment with dopaminergic agents (including L-Dopa and dopamine receptor agonist medications) for <3 months in total but not within 2 months of the Baseline Visit. Prior and concurrent use of MAO-B inhibitors is permitted if use was initiated >90 days before the Baseline Visit and the dosage will remain stable for the duration of the trial (ie, no change in the MAO-B inhibitor dose is permitted during the trial).
11.	Subjects who are willing and able to refrain from any PD medications that are not permitted by the protocol (including dopaminergic agents) throughout participation in the trial.

Abbreviations: ICF = informed consent form, IMP = investigational medicinal product, L-Dopa = levodopa, MAO-B = monoamine oxidase B, MDS-UPDRS = Movement Disorder Society-Unified Parkinson's Disease Rating Scale, PD = Parkinson's disease.

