7.3 Individual Subject Discontinuation

After treatment assignment, a subject may stop treatment permanently for a variety of reasons. Treatment discontinuation may be initiated by a subject who is not satisfied with treatment or may become medically necessary due to AEs, required treatment with a disallowed medication or therapy, or other issues, as determined by the investigator.

A subject may discontinue the IMP for any of the following reasons:

- Adverse event
- Death
- Worsening of PD symptoms to such an extent that, in the judgment of the investigator, the subject requires additional anti-PD medications
- Treatment with prohibited concomitant medications
- Noncompliance with the study schedule
- Noncompliance with the study drug
- Withdrawal by subject
- Pregnancy
- Physician decision

If a subject discontinues the IMP due to an AE, the investigator or other trial personnel will make every effort to follow the event until it has resolved or stabilized.

All subjects have the right to withdraw consent for further participation in the trial at any time without prejudice. Subjects cannot withdraw consent for use of data that have already been collected as part of the trial but can withdraw consent for future

participation. The investigator can also discontinue a subject from the trial at any time if medically necessary. Unless the subject provides written withdrawal of consent or there is other written documentation by the investigator confirming the subject's verbal intent to completely withdraw from the trial, subjects should be followed for all protocol-specified evaluations and assessments, if possible.

Complete withdrawal of consent requires a subject to refuse of ALL of the following methods of follow-up:

- Participation in all follow-up procedures specified in the protocol (whether in-clinic or by telephone)
- Participation in a subset of protocol specified follow-up procedures (by a frequency schedule and method, as agreed by subject and staff)
- Contact of the subject by trial personnel, even if only by telephone, to assess current medical condition, and obtain necessary medical or laboratory reports relevant to the trial's objectives
- Contact of an alternative person(s) who has been designated in source records as being available to discuss the subject's medical condition, even if only by telephone, mail, or e-mail (eg, family, spouse, partner, legal representative [as defined per local regulations], friend, neighbor, or physician)

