3.2.8. Prior Medications, Concomitant Medications and Medications Taken Post Last Dose of IMP

Prior medications are those medications taken prior and ended prior to the initiation of IMP. These medications will be captured in the CONCOMITANT MEDICATIONS eCRF.

Concomitant medications are those medications taken on or after the initiation of IMP. These medications include those medications started before the initiation of IMP and continuing post Day 1. Medications that start after the last dose of IMP until the end of protocol-specified reporting period will be classified as taken post last dose and will not be considered concomitant. These medications will be recorded in the eCRF. The investigator will record all medications and therapies (including vaccines, over-the-counter or prescription medicines, vitamins, and/or herbal supplements) that are used by the subject from 30 days before the informed consent form (ICF) is signed through the end of the Safety Follow-up Period (Week 31 or early termination). The investigator will also record all medications and therapies taken or received by a subject for treatment of an AE or that cause an AE through Week 31 or early termination.

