5.9.3.4. Impact of Missing Values Handling

Whilst every effort will be made to prevent avoidable missing values during the study conduct ([National Research Council, 2010](#)), it is unrealistic to expect no missing values in clinical trials. The impact of missing values on the analysis results will be assessed by the sensitivity analyses described below.

Under Missing at Random (MAR) Assumption

Multiple imputation (MI) will be performed to replace each missing value with a set of plausible values that represent the uncertainty about the correct value to impute. The Markov chain (MCMC) method will be utilized for the mITT set. SAS PROC MI will be used to generate 27 possible imputed datasets: Each of these datasets will be analyzed using PROC MIXED in SAS using the MMRM model as described in [Section 5.9.2](#). The results of the analyses of the datasets will be combined using PROC MIANALYZE to produce an inferential result.

Considerations of Data Potentially Missing Not at Random (MNAR)

A pattern mixture model (PMM) approach will be used to address potentially MNAR patterns. The following three patterns of subjects in the mITT set will be considered:

- 1) Subjects with no missing values from discontinuation or from initiation of prohibited Parkinson's disease concomitant mediation during treatment period.
- 2) Subjects with missing values from the types of ICEs below will be considered having MNAR
 - a. Subjects who discontinue due to reasons, as recorded on the eCRF, of lack of efficacy, adverse events associated with motor symptoms of Parkinson's disease, physician decision, and withdrawal by subject.
 - b. Subjects who initiated concomitant Parkinson's disease medications (ATC classifications of ADAMANTANE DERIVATIVES, DOPAMINE AGONISTS, MONOAMINE OXIDASE B INHIBITORS, OTHER ANTI-PARKINSON DRUGS, OTHER DOPAMINERGIC AGENTS, or DOPA AND DOPA DERIVATIVES) after the first dose of IMP and prior to the last dose of IMP with a use duration of 7 days or more will be considered having a potential confounding ICE. The efficacy data post ICE will be treated as missing with the missing pattern of MNAR.

The MNAR cases will be identified and documented prior to database lock and unblinding ([Section 9.5](#)).

- 3) Subjects with missing values from the type of ICEs below will be considered as having MAR

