5.10. Key Secondary Efficacy Analyses

5.10.1. Secondary Estimand 1

The key research question for the first secondary efficacy variable will be addressed with an estimand based on the following attributes:

- 1) Treatments: treatments as randomized regardless of the actual treatment received or the final dose level achieved following the titration steps.
- 2) Target study population of interest: subjects in the modified intent-to-treat (mITT) population regardless the completion status of dose titration steps.
- 3) Endpoint (variable) of interest: change from baseline to Week 26 in the MDS-UPDRS Part II Score.
- 4) Population level summary of interest: estimated mean difference between each tavapadon (CVL-751) dose group and placebo group in the endpoint of interest.
- 5) Strategy for Intercurrent events (ICEs): a hypothetical strategy will be used to address intercurrent events (ICEs) of potential death, treatment discontinuations, missed visits/assessments, and start of prohibited concomitant Parkinson's disease medications (see definitions in [Section 5.9.1](#)). The data after treatment discontinuations or after the start of prohibited concomitant Parkinson's disease treatments will be censored under the hypothetical strategy.

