5.16. Protocol Deviations

All protocol deviations will be reviewed by the project team prior to database lock and unblinding to identify subjects with important protocol deviations. The number and percentage of subjects with important deviations will be tabulated by treatment and further tabulated by category and treatment. All deviations from the protocol will be listed by category along with a description and any additional comments.

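### SAP 5.9.1 censors data after a newly started MAO-B inhibitor but, read literally, keeps data after a prohibited dose increase of one already in use at Baseline (minor; one clause fixes it)

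*SAP*

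**What the plan says.** Inclusion 10 (Protocol 5.1) accepts an MAO-B inhibitor begun more than 90 days before Baseline, provided the dose stays stable: "no change in the MAO-B inhibitor dose is permitted during the trial".

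SAP 5.9.1 applies a hypothetical strategy to death, treatment discontinuation, missed assessments and the start of prohibited Parkinson's disease medication. It defines that medication by ATC class, names MAO-B inhibitors among the classes, and limits it to drugs "started after the first dose of IMP and prior to the last dose of IMP with duration of use 7 days or more". Later data are censored. The stated aim is: "The hypothetical strategy allows the study to assess the effect of tavapadon treatment without the confounding effect of prohibited concomitant" Parkinson's disease treatment.

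The MNAR sensitivity analysis (SAP 5.9.3.4, pattern 2b) uses the same trigger: medication initiated "after the first dose of IMP and prior to the last dose of IMP with a use duration of 7 days or more". Both key secondary estimands (SAP 5.10) refer back to the 5.9.1 definition, and there too data after prohibited Parkinson's "disease treatments will be censored under the hypothetical strategy". SAP 3.2.8 separates drugs by when they began. Of concomitant medications it says: "These medications include those medications started before the initiation of IMP and continuing post Day 1". A background MAO-B inhibitor falls in that group.

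**The concern.** A new MAO-B inhibitor taken for a week leads to censoring. A forbidden increase in an existing one does not, although both add symptomatic treatment that the trial does not allow. The estimand's definition therefore falls short of its own stated aim. Subjects who worsen are the natural candidates for a raised dose. If that happens more often on placebo, the retained Week 26 values would make placebo look better than it would without the extra treatment, and the tavapadon effect would be diluted. The same wording carries into both key secondary endpoints and the MNAR sensitivity analysis.

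**Working it through.** **1. Does any other provision remove these data?**

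| Provision | Effect on a subject who raises a background dose and stays on IMP |
|---|---|
| SAP 5.9.1, started after first dose | Not met: the drug was begun before Baseline |
| SAP 5.9.3.4, pattern 2b | Same trigger, not met |
| SAP 5.9.2, MMRM | Adjusts for baseline MAO-B use only |
| Protocol 7.3: "A subject may discontinue the IMP for any of the following reasons" | Optional; data are censored only if IMP is actually stopped |
| Protocol Table 7 | No row for a changed MAO-B inhibitor dose |
| SAP 5.16: "The number and percentage of subjects with important deviations will be tabulated by treatment" | Deviations are tabulated and listed; no data are removed |
| SAP 5.9.4, subgroup by MAO-B use | Removes nothing, but non-users have no background dose to raise |

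On the plain wording, nothing censors these data.

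**2. The plan's own sample size.** Inputs (SAP 1.2): difference 4, SD 9, two-sided alpha 0.025, power 90%, dropout 27%.

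- Normal approximation: n = 2 × (9/4)² × (2.2414 + 1.2816)² = 125.7, so 126 per arm; 126/0.73 = 172.6, so 173.
- t-test version: 127 per arm; 127/0.73 = 174.0. The planned 174 is reproduced.

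The primary test of 15 mg uses the full 0.05 (SAP 5.4; Protocol 9.2 also states 0.05). With 127 evaluable per arm:

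- SE = 9 × √(2/127) = 1.129
- power = Φ(4/1.129 − 1.96) = 94.3%

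**3. Illustrative dilution.** The documents give neither the total of MAO-B users nor the number of dose raises nor the effect of a raise. Assume that k more placebo than tavapadon subjects have a raised dose in the Week 26 data, each gaining g points. The shift is k × g/127, and power is Φ((4 − shift)/1.129 − 1.96).

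| k | g | Shift (points) | Power at 0.05 |
|---|---|---|---|
| 1 | 2 to 4 | 0.016 to 0.031 | about 94% |
| 5 | 2 | 10/127 = 0.079 | 93.5% |
| 5 | 4 | 20/127 = 0.157 | 92.5% |

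Power reaches 90% when the shift is 4 − 1.129 × (1.96 + 1.2816) = 0.339 points. That needs 0.339 × 127/4 = 10.8 (11 subjects) at a 4-point gain, or 0.339 × 127/2 = 21.5 (22 subjects) at a 2-point gain. Over a wider range, a 1% placebo excess gaining 1 point gives 94.2%, and a 10% excess gaining 5 points (shift 0.5) gives 87.3%.

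**4. Cost of censoring.** If 5 placebo subjects lost their Week 26 value, SE = 9 × √(1/122 + 1/127) = 1.141 (+1.0%) and power is 93.9%. If 10 did, SE = 9 × √(1/117 + 1/127) = 1.153 (+2.1%) and power is 93.4%. These are upper bounds on the loss, because the MMRM still uses the earlier visits.

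**The case against.** The strongest objection is that the gap may not exist in the data. Protocol 6.5.1 records a dose and start and end dates for each medication. A site might well enter a raised dose as a new row dated after first IMP, and a program keyed on that date would then flag it. This stands as a possibility, but neither document states the convention. Censoring in the primary analysis would then depend on how a site logs a change: an unchanged dose entered again could be censored, and a true increase kept on one row could be missed. The list of identified MNAR cases (SAP 9.5) was not available, so it cannot settle which cases were flagged.

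Second, the protocol's own intercurrent event is the start of prohibited medication (Protocol 9.4.1), and a dose change is a breach of Inclusion 10 rather than a Table 7 item. That is true, so the SAP does not contradict the protocol's event. But Table 7 does not list selective MAO-B inhibitors at all, and SAP 5.9.1 already treats starting one as an event. It is guided by the confounding it wants to remove, and an increase in the same drug belongs with it.

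Third, worsening that needs more anti-Parkinson medication is a listed reason to stop IMP, and data after stopping are already censored. This narrows the group affected. The non-user subgroup in SAP 5.9.4 gives a partial check for the primary and both key secondary endpoints, unless the 10% subgroup-size rule leads to it being redefined or dropped.

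Fourth, pattern 2b matters less than it seems. SAP 5.9.3.4 imputes placebo MNAR cases as MAR, so reclassifying a placebo subject there changes nothing. This is correct.

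**Conclusion.** The point holds as a minor, cheap improvement to the estimand definition. Read literally, SAP 5.9.1 keeps data after one kind of prohibited Parkinson's treatment change, and no other rule removes them while the subject stays on IMP.

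The size is unknown and probably small, since only background MAO-B users who breach Inclusion 10 and continue IMP can contribute. The direction is toward no difference only if raises are more common on placebo, which is plausible but not documented. The figures above rest on an assumed gain per raise, an assumed placebo excess and 127 evaluable subjects per arm.

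A reader might infer a false-positive risk, or that the primary result is unreliable. The documents support neither: nothing in them suggests that raises would favour tavapadon, and it takes 11 to 22 excess placebo subjects under the 2 to 4 point assumption to bring power below 90% at the 0.05 level used for testing. A reader might also infer that every dose raise certainly escapes the rule. That depends on an eCRF convention that is not stated.

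**What to change.** In SAP 5.9.1, add to the definition of prohibited Parkinson's medication: or a dose increase lasting 7 days or more of an MAO-B inhibitor in use at Baseline. State that cases are identified blinded, from the eCRF dose and date records, before database lock, and that re-logging an unchanged dose is not an event. The key secondary estimands follow through their reference to 5.9.1.

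Mirror the clause in pattern 2b of 5.9.3.4 for consistency. There it changes the imputation only for tavapadon-arm subjects, who would move to jump-to-reference.

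No protocol change and no new data are needed, and SAP 5.9.3.4 already plans a case review before lock. The price is a few more censored observations: the standard error rises by at most about 1% to 2% if 5 to 10 placebo subjects lose their Week 26 value.

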5.9.2. Main Analytical Approach

The change from baseline to each study visit in MDS-UPDRS Part II and III combined score will be summarized by visit and treatment group. A mixed model repeated measures (MMRM) analysis will be used to analyze the data from all post-randomization timepoints up to Week 27 with fixed effect of treatment group, visits, interaction between treatment group and visit, and baseline MAO-B inhibitor use. The baseline value of MDS-UPDRS Part II and III combined score will also be included as a covariate. Subject will be included as a random effect. An unstructured covariance structure will be used for the repeated measures. If the unstructured covariance matrix results in convergence issue, the heterogeneous Toeplitz covariance structure followed by the heterogeneous first-order autoregressive (AR(1)) structure will be used. The Kenward-Roger approximation will be used to estimate the denominator degrees of freedom. The difference between each active dose and placebo at the endpoint visit (Week 26) will be estimated based on the Least Squares Mean (LSMean) difference derived from the MMRM with the associated 95% confidence intervals (CI) and P-values. A Cohen's D value will also be derived as the ratio of the estimated difference to the population standard deviation at each visit estimated from the model (the square root of the diagonal elements of the estimated covariance matrix). The missing values, including missing due to missed visits or early termination due to COVID-19 control measures, are assumed to be missing at random (MAR) in the main MMRM analysis. Sensitivity analyses will be performed to assess the impact of deviation from MAR assumptions on the analysis results. Time curve plots will be presented for both raw Mean (SEM) and LSMean (SE).

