9.2 Sample Size Determination

A total of 522 subjects are planned to be randomized in a 1:1:1 ratio to the tavapadon 5mg QD, tavapadon 15 mg QD, or placebo QD treatment group. A sample size of 174 subjects per group will provide at least 90% power to detect a change in the primary outcome measure (change from baseline to endpoint in the MDS-UPDRS Parts II and III combined score) of 4 points, with a standard deviation of 9, 2-sided alpha level = 0.05, and assuming a 27% dropout rate.

In the event of higher than anticipated early terminations due to COVID-19 or other reasons, Cerevel may extend enrollment in order to maintain the planned statistical power.

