9.4.1 Efficacy Analyses

The efficacy endpoints will be assessed for each of the 2 dose levels of tavapadon versus placebo. A hierarchical testing procedure is planned for the primary and key secondary endpoints, in the following order, to control the Type I error rate at the 0.05 level (2-sided).

1. Tavapadon 15 mg QD versus placebo on the primary endpoint

2. Tavapadon 5 mg QD versus placebo on the primary endpoint
3. Tavapadon 15 mg QD versus placebo on the key secondary endpoint of MDS-UPDRS Part II score change from baseline
4. Tavapadon 15 mg QD versus placebo on the key secondary endpoint of percentage of responders on the PGIC score
5. Tavapadon 5 mg QD versus placebo on the key secondary endpoint of MDS-UPDRS Part II score change from baseline
6. Tavapadon 5 mg QD versus placebo on the key secondary endpoint of percentage of responders on the PGIC score

The analysis methods for the primary and secondary endpoints are summarized in [Table 9](#). Additional details will be provided in the statistical analysis plan.

Table 9 Efficacy Analysis

Endpoint	Statistical Analysis Methods
Primary	
The primary efficacy endpoint (the change from baseline to endpoint in the MDS-UPDRS Parts II and III combined score) will be analyzed using an MMRM. The change from baseline at each postbaseline timepoint will be included in the MMRM as repeated measures. The baseline score will be included as a covariate, and treatment group, visit, the interaction between treatment group and visit, and the stratification factor (concurrent use of MAO-B inhibitor; yes/no) will be included as fixed factors. An unstructured covariance structure will be utilized. The difference between each tavapadon dose level and placebo at endpoint will be estimated based on the LSMeans from the MMRM. A hypothetical strategy will be used to address ICEs of potential death, treatment discontinuations, missed visits/assessments, and start of prohibited concomitant medications. The data after treatment discontinuations or after the start of prohibited concomitant medications will be censored under the hypothetical strategy. The missing values are assumed to be MAR in the primary analysis, including missing due to COVID-19 control measures. Sensitivity analyses will be performed to assess the impact of deviation from MAR assumptions on the analysis results.

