1.2. Sample Size Considerations

A sample size of 174 subjects per group will provide 90% power to detect a change in the primary outcome measure (change from baseline to endpoint in the MDS-UPDRS Parts II and III combined score) of 4 points, with a standard deviation of 9, 2-sided alpha level = 0.025, and assuming a 27% dropout rate.

In the event of higher than anticipated early terminations due to COVID-19 or other reasons, Cerevel may extend enrollment in order to maintain the planned statistical power.

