5.4. Multiplicity Adjustment

A graphical approach depicted below is utilized to illustrate the hierachal multiple testing strategy planned for the hypotheses described above to control the overall Type I error rate. The primary endpoint of the tavapadon 15 mg QD will be compared with that of placebo (H_1) with full α of 0.05 and, if successful, the available α will be passed along fully ($r=1$) to the comparison of the primary endpoint of tavapadon 5 mg QD with placebo (H_2). If H_2 is successful, the full α will be available to the secondary hypothesis H_3 . The sequence will continue until H_6 or until the sequence breaks with no α remaining available.

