5.10.1.1. Main Analytical Approach

Similar to the analysis of the primary efficacy variable, the change from baseline to each study visit in MDS-UPDRS Part II score will be summarized by visit and treatment group. A mixed model repeated measures (MMRM) analysis will be used with fixed effect of treatment group, visits, and interaction between treatment group and visit, and MAO-B inhibitor use. The baseline value of MDS-UPDRS Part II score will be included as a covariate. Subject will be included as a random effect. An unstructured covariance structure will be used for the repeated measures. If the unstructured covariance matrix results in convergence issue, the heterogeneous Toeplitz covariance structure followed by the heterogeneous first-order autoregressive (AR(1)) structure will be used. The Kenward-Roger approximation will be used to estimate the denominator degrees of freedom. The difference between each active dose and placebo at the endpoint visit (Week 26) will be estimated based on the Least Squares Mean (LSMean) difference derived from the MMRM with the associated 95% confidence intervals (CI) and P-values. A Cohen's D value will also be derived as the ratio of the estimated difference to the population standard deviation at each visit estimated from the model (the square root of the diagonal elements of the estimated covariance matrix). The missing values, including missing due to missed visits or early termination due to COVID-19 control measures, are assumed to be missing at random (MAR) in the main MMRM analysis. Sensitivity analyses will be performed to assess the impact of deviation from MAR assumptions on the analysis results. Time curve plots will be presented for both raw Mean (SEM) and LSMean (SE).

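### The MMRMs for the primary and Part II endpoints fit one baseline slope to all eight visits; a prespecified baseline-by-visit term costs almost nothing and helps at Week 26 if that slope varies.

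*SAP*

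**What the plan says.** SAP 5.9.2 specifies fixed effects for treatment, visit, treatment by visit and MAO-B inhibitor use, with an unstructured covariance. On baseline it says only: "The baseline value of MDS-UPDRS Part II and III combined score will also be included as a covariate". SAP 5.10.1.1 repeats this form for the first key secondary endpoint: "The baseline value of MDS-UPDRS Part II score will be included as a covariate". Protocol 9.4.1, Table 9 agrees: "The baseline score will be included as a covariate". Neither document contains a baseline-by-visit term.

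Protocol 8.2.1 schedules the post-baseline MDS-UPDRS at Weeks 5, 8, 11, 14, 18, 22, 26 and 27. SAP 4.1.3 and 5.9.2 take the tested contrast at Week 26.

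The multiple imputation code in SAP 9.6.1 puts the baseline score and every visit score into one joint model. Baseline can therefore relate differently to each visit in the imputation. The completed data sets are then analysed with the MMRM of 5.9.2.

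**The concern.** A single baseline term in a model for change assumes that baseline predicts change equally at Week 5 and at Week 26. The plan leaves every variance and covariance among the post-baseline visits free but fixes this one relation, and gives no reason.

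If the slope does vary, the pooled slope adjusts imperfectly at Week 26. The uncorrected part goes into the Week 26 residual variance. It widens the confidence interval and, because SAP 5.9.2 takes the SD for Cohen's D from the model, shrinks the reported effect size. The MAR handling of dropout would also rest on a mean model that does not fit each visit. That could matter here because 27% dropout is assumed and Protocol 7.3 lists worsening PD symptoms as a reason for stopping, so dropout linked to severity is plausible.

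**Working it through.** **1. The plan's own figure.** Protocol 9.2 states: "A sample size of 174 subjects per group will provide at least 90% power to detect a change in the primary outcome measure", with an effect and spread given as "combined score) of 4 points, with a standard deviation of 9". With n = 2(z_α/2 + z_β)² × SD²/δ², SD 9 and δ 4, the multiplier is 2 × 81/16 = 10.125.

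- α = 0.025 two-sided, as in SAP 1.2 ("with a standard deviation of 9, 2-sided alpha level = 0.025, and assuming a 27% dropout rate"): 126 per arm, and 126/0.73 gives 173. The t-based version gives 127, then 174. The stated 174 is reproduced.
- α = 0.05 two-sided, as in Protocol 9.2 ("with a standard deviation of 9, 2-sided alpha level = 0.05, and assuming a 27% dropout rate"): 107 per arm, then 147. So 174 exceeds the minimum.

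The two documents differ on this α, which is a separate matter. SAP 5.4 tests at 0.05 ("will be compared with that of placebo (H_1) with full α of 0.05"), so 0.05 is used below. With 174 × 0.73 = 127 completers per arm, power is 94.3%.

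**2. Closed form, complete data.** Let d be the gap between the Week 26 slope and the pooled slope, and SDb the baseline SD. Taking 9 as the residual SD, the variance of the Week 26 contrast is (2/n)(81 + d²SDb²) with a common slope and (2/n)(81) with the interaction. Both d and SDb are assumptions; the documents give neither.

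- d = 0.10, SDb = 9: 0.81/81 = 1.0% on the variance; √1.010 gives 0.5% on the SE; 127 × (1 − 81/81.81) ≈ 1 completer per arm.
- d = 0.20, SDb = 13: 6.76/81 = 8.3% on the variance; √1.083 gives 4.1% on the SE; 127 × (1 − 81/87.76) ≈ 10 completers per arm.

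Power with the common slope, against 94.3% with the interaction:

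| d | SDb | Power |
|---|---|---|
| 0.10 | 12 | 94.0% |
| 0.20 | 12 | 92.8% |
| 0.20 | 13 | about 92.4% |
| 0.20 | 16 | 91.6% |
| 0.30 | 16 | 87.8% |

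The last two rows lie outside the 9 to 13 range for SDb and show how far the assumptions must be pushed to bring power below 90%.

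**3. Simulation with dropout.** Three arms of 174, eight visits, unstructured covariance, true effect −4, 300 replicates per scenario. Dropout was about 27% when completely random and about 21% when it depended on baseline and last score (MAR). Residual correlation was assumed to fall from about 0.96 one week apart to 0.58 at 22 weeks. The SE ratio is with over without the interaction, at Week 26.

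| Slope, Week 5 to Week 26 | SDb | SE ratio, random dropout | SE ratio, MAR dropout | Bias under MAR: common slope / interaction |
|---|---|---|---|---|
| −0.3 throughout | 12 | 1.0005 | 1.0004 | 0.05 / 0.05 |
| −0.2 to −0.3 | 12 | 0.997 | 0.995 | 0.06 / 0.03 |
| −0.1 to −0.4 | 12 | 0.971 | 0.966 | 0.11 / 0.03 |
| −0.1 to −0.4 | 16 | 0.949 | 0.944 | 0.11 / 0.02 |
| 0 to −0.5 | 12 | 0.922 | 0.914 | 0.14 / 0.02 |

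The two methods agree in scale. In the third row, under random dropout, the pooled slope was −0.229, so d = 0.171. The closed form then gives 1/√(1 + (0.171 × 12)²/81) = 0.975, against 0.971 simulated.

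The bias column needs caution. The Monte Carlo error of a single bias is about 1.03/√300 = 0.06. Under random dropout the two models' biases differed by at most about 0.03, which gauges the noise in the comparison. The MAR differences of 0.08 to 0.12 under moderate and strong drift exceed that; the mild-drift difference does not.

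**4. Cost.** Eight visits add 8 − 1 = 7 parameters. With equal slopes the SE rose by about 0.05% (first row).

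**The case against.** The strongest reply is that this is a preference. The main-effect form is the same in both documents, and with complete data randomisation keeps its contrast unbiased. Power stays above the planned 90% over the whole stated range (d up to 0.20, SDb up to 13). All of that stands.

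A reader might infer from the titration schedule that the slope must drift, since Week 5 (Day 35) comes before either arm reaches its randomised dose. The documents do not support so much. By Protocol 4.1.2 the 5 mg dose starts on Day 41 and the 15 mg dose on Day 73. Seven of the eight visits in the 5 mg arm and six of eight in the 15 mg arm therefore fall at the randomised dose, and placebo has no change. Titration makes drift possible; it does not establish it or its size.

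The missing-data concern is also partly covered. The imputation in SAP 9.6.1 is not tied to one slope, and jump-to-reference and completer analyses are planned. These are sensitivity analyses, however, and the primary MMRM still uses the common slope.

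Finally, the term is less cheap in small samples. SAP 5.9.4 reuses this model in subgroups that may be as small as 10% of mITT. That is about 52 subjects if mITT is near 522, with 8 × 9/2 = 36 covariance parameters already to estimate. This stands and limits the scope of the fix.

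**Conclusion.** A cheap improvement with a conditional gain, not a flaw that threatens the primary result. The restriction to one slope is certain from the text; whether it costs anything is not. For d of 0.10 to 0.20 and SDb of 9 to 13, the Week 26 SE is inflated by about 0.5% to 4%. In simulation the term lowered the SE by 0.3% to 0.5% under mild drift, 3% to 6% under moderate drift and 8% to 9% under strong drift, and not at all with equal slopes. The bias under baseline-related dropout was about 0.1 point on a 4-point effect, and only under assumed moderate to strong drift.

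Two stronger readings should be resisted: that the planned contrast is biased as it stands, and that precision is certainly being lost. Either would need evidence on how the slope behaves over time, and the documents contain none. The sizes above are for the combined score. No SD is given for Part II, so only the direction of the argument carries over.

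The case rests on asymmetry: almost no loss if the term is unnecessary, and modest protection if it is needed.

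**What to change.** Before database lock and unblinding:

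- Add baseline score by visit as a fixed effect in the full-population models of SAP 5.9.2 and 5.10.1.1.
- Use the same model on the multiply imputed data sets, so that it matches the visit-specific baseline relations allowed by SAP 9.6.1.
- Record the difference from Protocol Table 9.
- State how far the term carries, because SAP 5.9.4, 5.12, 5.14.2 and 5.14.3 refer back to 5.9.2. The main-effect form may be kept for small subgroups where the larger model does not fit stably.

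No new data are needed. The cost is 7 parameters per model, about 0.05% on the Week 26 SE if the slopes are equal, and one documented protocol-SAP difference. If the sponsor prefers to leave the primary model unchanged, the term can be prespecified as a sensitivity analysis. It should not be introduced after unblinding, when it would look data-driven.
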